## **6.2 During radiochemotherapy**

- Laboratory examination weekly: haematology: Hb, Ht, platelets, leucocytes; cchemistry: Na, K, Ca, Alb, Creatinine, Bilirubin, gGT, AF, ASAT, ALAT, LDH. Creatinin clearance if plasma creatinine > 100 umol/l.
- Morbidity according to CTCAE criteria version 3 (addendum 2, page 23)
  - signs of early toxicity (eg skin)
  - monitoring of other radiotherapy-related toxicity (bowel, GU)

During radiotherapy patients will be seen weekly by the radiation oncologist and medical oncologist to monitor morbidity and treatment related toxicity

## **6.3 During first follow-up after radiotherapy at 4 and 8 weeks and response assessment at 12 weeks.**

The patient will be seen 4 and 8 weeks after the end of the radiochemotherapy by the radiation oncologist and gynaecologist and physical and gynaecological examination will be performed. At that time short term morbidity must be assessed and progression of disease must be ruled out. At 12 weeks after the end of the radiochemotherapy response assessment will be done by the radiation oncologist and gynaecologist. Special attention is to be given to the vulva and groin area by visual examination and palpation in search of residual disease. Lesions suspicious for recurrence are to be biopsied. Response will be reported according to RECIST criteria (addendum 2, page 23).

## **6.4 After surgery**

After the surgical procedure the following parameters will be recorded:

- Surgery associated morbidity
- Formation of urostomy/colostomy or reconstructive surgery
- Need for antibiotics
- Lymphedema of the legs or other morbidity involving the legs (eg infection)
- Duration of surgery
- Long-term morbidity: this is defined as morbidity as from the day the patient left the hospital. This will be monitored from the first-follow-up visit
- Length of hospitalization

## 6.5 During follow-up

In the first two years after treatment patients will be closely monitored. Follow-up visits will take place every three months (by the radiation oncologist and/or gynaecologist) as is normal standard of care and the following examinations will take place:

- Physical and gynaecological examination. Special attention is to be given to the vulva and groin area by visual examination and palpation in search of recurrent disease. Lesions suspicious for recurrence are to be biopsied.
- Long-term morbidity: this is defined as morbidity as from the day the patient left the hospital. This will be monitored from the first-follow-up visit

From two to five years after registration patients will be seen every 6 months and apart from the medical history (with explicit inquiries about experienced morbidity) the above mentioned examinations are required. No routine laboratory investigations are performed.

## 6.6 Summary Table

Required investigations	Prestudy	After initial surgery*	During radiochemotherapy	After radiochemotherapy	After secondary surgery**	During follow up
						yr. 1-2: 3-monthly yr 2-5: 6-monthly
Day	-28 tot 0	-28 tot 0	Start day 0  weekly	4, 8 and 12 weeks after last radiochemotherapy	> 12 weeks after last radiochemotherapy	
History	X 1					
Phys/gyn exam	X 1/ 2			X 1/2		X 1/2
WHO	X 1		X 2/ 3	X 2		
TNM	X 1					
Photo	X 1			X 2		
Chest X-ray	X 1					
CT/MRI/US	X 1			X 1/2 ***		
Haematology	X 1		X 2/ 3	X 1		
Biochemistry	X 1		X 2/ 3	X 1		
Path lymph nodes		X 1			X 1	
Path primary tumor	X 1				X 1	
Short-term morb		X 1	X 2/ 3	X 2	X 1	
Long term morb						X 1/2

\* Only when upfront surgery is performed for clinically (and pathologically confirmed) positive groin lymph node metastases

\*\* Only when salvage surgery for the primary or groin dissection is performed

\*\*\* Optional

- 1) gynecologic oncologist
- 2) radiation oncologist
- 3) medical oncologist

 Haematology: Hb, Ht, platelets, leucocytes  
Chemistry: Na, K, Creatinin, ureum, Bilirubin, gGT, AF, ASAT, ALAT, LDH.  
Creatinin clearance if plasma creatinin > 100 umol/l.

## **7 Criteria of evaluation**

**Evaluable for response:** all eligible patients will be included in the response rate calculation.

### **7.1 Assessment of locoregional tumor response**

Twelve weeks after the full course of radiochemotherapy the patient will be assessed by the radiation oncologist and gynecologic oncologist. A photograph of the tumor with an adjacent ruler must be taken. The residual primary tumor will be measured in two directions and the longest diameter is assessed according to the RECIST criteria (see addendum 2). In case a clinical complete response is confirmed the groins will be treated as described in section 5.3 whenever no upfront debulking was performed. A complete response of the groin lymph nodes is defined as no residual disease in the groins after radiochemotherapy and surgery. No further surgery for the vulvar area is considered. Only when there is doubt about the clinical complete response or no agreement between gynecologist and radiation oncologist can be achieved, a mapping procedure must be performed to confirm the complete response also pathologically. In all other cases salvage surgery must be considered and if necessary reconstructive surgery or exenterative surgery with stoma formation must be considered.

### **7.2 Short-term morbidity**

This is defined as any treatment related morbidity until the end of radiotherapy or discharge from the hospital. Any toxicity/morbidity should be reported according to the CTC guidelines version 3 (addendum 2). Most common complications are: skin toxicity, infections, gastrointestinal toxicity, and urinary toxicity. Surgical morbidity can consist of excessive blood loss during surgery (>500ml), damage/laceration to femoral vein, artery or nerve or wound breakdown after surgery and/or severe infections (sepsis).

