### **2.2 secondary objectives**

The secondary objective would be to determine short-term morbidity defined as desquamation of the skin, infection, long-term morbidity defined as edema, fibrosis, the incidence of fecal and or urinary continence, and or incidence of reconstructive surgery performed and treatment related mortality. Longterm morbidity and the rate of locoregional recurrences will be evaluated at 24 months after the end of radiochemotherapy.

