#### **Secondary endpoints**

- morbidity and treatment related toxicity
- incidence of fecal and/or urinary continence and/or reconstructive surgery performed
- locoregional recurrence rate at 24 months after the end of radiochemotherapy

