### **7.3 Long-term morbidity**

Long-term morbidity is defined as all morbidity which has developed after the end of the radiochemotherapy or discharge from hospital. The most common long-term morbidity in this disease after treatment is lymphedema of the legs, pain, infection (cellulitis, erysipelas), need for antibiotics for leg/groin infection, radiation enteritis. All long-term morbidity should be reported according to the RTOG/EORTC guidelines (addendum 3).

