### Safety Monitoring

Adverse events will be monitored on an ongoing basis and their frequencies reported semi-annually. Toxic effects will be categorized using the NCI Common Terminology Criteria for Adverse Events, Version 3.0. The worst event for each patient will be described. Both events related and unrelated to treatment will be captured.

Clinical and laboratory data will be tabulated and compared to normal ranges for the institution.

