## **12 Reporting adverse events**

### **12.1 Definitions**

An **Adverse Event (AE)** is defined as any untoward medical occurrence or experience in a patient or clinical investigation subject which occurs following treatment regardless of the dose or causal relationship. This can include any unfavourable and unintended signs (such as rash or enlarged liver), or symptoms (such as nausea or chest pain), an abnormal laboratory finding (including blood tests, x-rays or scans) or a disease temporarily associated with the use of the protocol treatment. (*ICH-GCP*).

A **Serious Adverse Event (SAE)** is defined as any undesirable experience occurring to a patient, whether or not considered related to the protocol treatment. Adverse events and adverse drug reactions which are considered as **serious** are those which result in:

- ◆ Death

- ◆ A life threatening event (i.e. the patient was at immediate risk of death at the time the reaction was observed)
  - ◆ Hospitalization or prolongation of hospitalization
  - ◆ Persistent or significant disability/incapacity
  - ◆ A congenital anomaly/birth defect
  - ◆ Any other medically important condition (i.e. important adverse reactions that are not immediately life threatening or do not result in death or hospitalization but may jeopardize the patient or may require intervention to prevent one of the other outcomes listed above)
- (ICH-GCP).

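### Section 7.2 limits short-term morbidity to treatment-related events, at odds with sections 2.2, 7.3, 8 and 12.1 and with its own next sentence, and may under-count short-term harm

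*Protocol*

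**What the plan says.** The definition of short-term morbidity in Protocol section 7.2 reads: "This is defined as any treatment related morbidity until the end of radiotherapy or discharge from the hospital". The sentence after it drops the causal limit: "Any toxicity/morbidity should be reported according to the CTC guidelines version 3 (addendum 2").

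The rest of the protocol treats the matter as follows:

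- Section 2.2 describes the secondary objective by type of event: "short-term morbidity defined as desquamation of the skin, infection, long-term morbidity defined as edema, fibrosis". Cause is not mentioned.
- Section 2.3 lists "morbidity and treatment related toxicity" as a secondary endpoint, so morbidity stands beside treatment-related toxicity and is not reduced to it.
- Section 7.3 sets no causal limit: "Long-term morbidity is defined as all morbidity which has developed after the end of the radiochemotherapy or discharge from hospital".
- Section 8, Safety Monitoring, states: "Both events related and unrelated to treatment will be captured".
- Section 12.1 defines an adverse event as one that "occurs following treatment regardless of the dose or causal relationship".

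Sections 5.2.1 and 12.2 also use relatedness, for capecitabine interruption and for late serious adverse event reports. Neither says who decides it or by what criterion.

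**The concern.** An endpoint definition decides which events enter the reported rate. Under 7.2, a short-term event that someone attributes to the tumour falls outside the endpoint. Under 2.2, section 8 and 12.1 the same event belongs to what is studied or recorded. Two analysts working from this protocol could each produce a defensible headline rate, and the rates could differ.

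Attribution is hard to make and hard to check in this population. Section 1.1 says that these tumours cause pain, discharge and bleeding by themselves and that involved nodes often ulcerate. Section 7.2 lists infections among the common complications, and in necrotic or ulcerated disease an infection can plausibly be put down to either cause. With one arm, no comparison rate shows how much of the morbidity is background disease.

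What is at stake is a secondary endpoint that bears on the trial's rationale. Section 1.6 sets this treatment against the morbidity of exenterative surgery, so a short-term harm rate that leaves out some events would flatter the new approach.

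**Working it through.** The protocol states no expected morbidity rate, attribution share or safety sample size, so there is no figure to reproduce. The check is a comparison of the text, then the direction and scale of the effect.

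**1. The passages side by side**

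| Place | What it covers | Causal limit? |
|---|---|---|
| 2.2 | Short-term morbidity, named by event type | No |
| 2.3 | Morbidity, listed beside treatment-related toxicity | Not on morbidity |
| 7.2, first sentence | Short-term morbidity, definition | **Yes** |
| 7.2, second sentence | Short-term reporting, CTC version 3 | No |
| 7.3 | Long-term morbidity, definition | No |
| 8, Safety Monitoring | Event capture, CTCAE version 3.0 | No, both kinds |
| 12.1 | Adverse event, definition | No |

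The first sentence of 7.2 stands alone, and it is the sentence that defines the endpoint.

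**2. Direction of the effect**

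Let *n* be the patients who started radiochemotherapy, which is the toxicity analysis set in section 8. Let *A* be those with at least one short-term event judged related, and *B* those whose short-term events were all judged unrelated.

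- Rate under the first sentence of 7.2: *A/n*
- All-cause rate: (*A* + *B*)/*n*
- Difference: (*A* + *B*)/*n* − *A/n* = *B/n*, which is zero or more

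The same holds at any severity threshold if only events at or above it are counted. The restriction can therefore lower the rate or leave it unchanged, but never raise it.

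**3. Scale of the effect**

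Each patient in *B* moves the rate by 1/*n*. At the full 68 patients of section 8 that is 1/68 = 1.5 percentage points. If accrual stops at the first-stage 42 it is 1/42 = 2.4 points. These figures assume that every patient accrued starts treatment.

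The number of patients in *B* is unknown, and nothing in the protocol bounds it usefully. An assumed share of unrelated *events* would not supply it either, because a patient with one related and one unrelated event is in *A* and still counts.

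**4. What it touches**

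The primary endpoint is complete locoregional remission at 12 weeks. The two-stage rule (42, then 68 patients) counts those responses only. Neither uses morbidity.

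**The case against.** The strongest reply is that little is lost. Section 8 captures unrelated events too, the second sentence of 7.2 asks for any toxicity, and all treated patients are in the analysis set, so an all-cause short-term rate can be tabulated from planned data. Treatment-related morbidity is also a recognised quantity in its own right, and the layout of attribution columns is ordinarily left to the statistical analysis plan.

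Most of that stands. The limit lies in the definition and not in data capture, which is why the repair is cheap. A related-only rate is worth reporting. But the protocol itself fixes the endpoint definition, and fixes it inconsistently. The second sentence of 7.2 does not cure the first: it leaves a related-only definition next to an all-cause reporting instruction.

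Two stronger readings are tempting and are not supported:

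- *That the changed causal rule is what stops short-term and long-term rates being compared.* The protocol plans no such comparison. The two rates also differ in time window and in grading scale, CTC version 3 against RTOG/EORTC. Removing the limit in 7.2 would not make them comparable. The long-term scale in Addendum 3 is itself a late radiation scale, so 7.3 should not be pressed as proof that every later event is counted whatever its cause.
- *That the protocol leaves the decision on relatedness to the treating team.* It names no one. Oncologists monitor morbidity weekly (6.2) and investigators sign the case report forms (11.2), so this is a natural inference, but it is not stated.

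**Conclusion.** The point holds as an inconsistency in how a secondary endpoint is defined. Section 7.2 restricts short-term morbidity to treatment-related events, while 2.2, its own next sentence, 7.3, section 8 and 12.1 impose no such restriction. In an uncontrolled trial with no stated rule for relatedness, a rate built on that definition may under-count short-term harm.

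The direction is certain: the related-only rate cannot exceed the all-cause rate. The amount cannot be estimated from the documents. A reader might multiply a guessed patient event rate by a guessed share of unrelated events to obtain a loss in percentage points. Neither input has a source in the protocol, and the product is at most a ceiling, because it treats every affected patient as having a single event.

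This is a modest point, worth making because the correction is simple. The primary endpoint, sample size and stopping rule do not change.

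**What to change.** In section 7.2, delete *treatment related*, so that short-term morbidity means all CTCAE version 3 events in the stated period, in patients who started radiochemotherapy. Report investigator-judged related events in a second column of the same table, and add a sentence saying who makes that judgement and by what rule.

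The cost is a wording change and one table column. No new data are needed, since section 8 already requires related and unrelated events to be captured. The downside is that the headline rate will include some symptoms of the tumour itself and look slightly less favourable. The second column lets the reader see how much of the total was attributed to treatment.

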### **7.3 Long-term morbidity**

Long-term morbidity is defined as all morbidity which has developed after the end of the radiochemotherapy or discharge from hospital. The most common long-term morbidity in this disease after treatment is lymphedema of the legs, pain, infection (cellulitis, erysipelas), need for antibiotics for leg/groin infection, radiation enteritis. All long-term morbidity should be reported according to the RTOG/EORTC guidelines (addendum 3).

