### RTOG/EORTC Late Radiation Morbidity Scoring Scheme

Use for toxicity occurring greater than 90 days after radiation therapy.

Grade									
Toxicity		0	1	2	3	4			
Bladder-Late RT Scoring	Morbidity	No change from baseline	Slight epithelial atrophy/minor telangiectasia (microscopic hematuria)	Moderate frequency/generalized telangiectasia/intermittent macroscopic hematuria	Severe frequency and dysuria/severe telangiectasia (often with petechiae); frequent hematuria; reduction in bladder capacity (< 150 cc)	Necrosis/contracted bladder (capacity < 100 cc)/severe hemorrhagic cystitis			
Bone-Late RT Scoring	Morbidity	No change from baseline	Asymptomatic; no growth retardation; reduced bone density	Moderate pain or tenderness; growth retardation; irregular bone sclerosis	Severe pain or tenderness; complete arrest of bone growth; dense bone sclerosis	Necrosis/spontaneous fracture			
Brain-Late RT Scoring	Morbidity	No change from baseline	Mild headache; slight lethargy	Moderate headache; great lethargy	Severe headaches; severe CNS dysfunction (partial loss of power or dyskinesia)	Seizures or paralysis; coma			
Esophagus-Late RT Scoring	Morbidity	No change from baseline	Mild fibrosis; slight difficulty in swallowing solids; no pain on swallowing	Unable to take solid food normally; swallowing semi-solid food; dilatation may be indicated	Severe fibrosis; able to swallow only liquids; may have pain on swallowing; dilation required	Necrosis/perforation; fistula			
Heart-Late RT Scoring	Morbidity	No change from baseline	Asymptomatic or mild symptoms; transient T wave inversion and ST changes; sinus tachycardia > 110 (at rest)	Moderate angina on effort; mild pericarditis; normal heart size; persistent abnormal T wave and ST changes; low QRS	Severe angina; pericardial effusion; constrictive pericarditis; moderate heart failure; cardiac enlargement; EKG abnormalities	Tamponade/severe heart failure/severe constrictive pericarditis			
Joint-Late RT Scoring	Morbidity	No change from baseline	Mild joint stiffness; slight limitation of movement	Moderate stiffness; intermittent or moderate joint pain; moderate limitation of movement	Severe joint stiffness; pain with severe limitation of movement	Necrosis/complete fixation			

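### The protocol gives conflicting time boundaries and grading scales for morbidity that first appears between the end of radiochemotherapy and day 90

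*Protocol*

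**What the plan says.** Section 7.2 closes the short-term window: "This is defined as any treatment related morbidity until the end of radiotherapy or discharge from the hospital". It names the scale in general terms: "Any toxicity/morbidity should be reported according to the CTC guidelines version 3 (addendum 2").

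Section 7.3 opens the long-term window at the same point: "Long-term morbidity is defined as all morbidity which has developed after the end of the radiochemotherapy or discharge from hospital". Its scale is different: "All long-term morbidity should be reported according to the RTOG/EORTC guidelines (addendum 3"). Addendum 3 heads that scheme with its range of use: "Use for toxicity occurring greater than 90 days after radiation therapy".

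Other parts of the Protocol draw the line elsewhere:

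- Section 6.3, on the visits 4 and 8 weeks after radiochemotherapy: "At that time short term morbidity must be assessed and progression of disease must be ruled out".
- Table 6.6 marks short-term morbidity in the column headed "4, 8 and 12 weeks after last radiochemotherapy". It marks long-term morbidity only in the follow-up column.
- Section 2.2 sorts by kind: desquamation and infection are short-term, edema and fibrosis long-term.
- Sections 6.4 and 6.5 start long-term morbidity on the day of hospital discharge.
- Section 8, Safety Monitoring, sets no time limit: "Toxic effects will be categorized using the NCI Common Terminology Criteria for Adverse Events, Version 3.0".

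**The concern.** Read together, 7.2, 7.3 and Addendum 3 call an event that first appears a few weeks after the last fraction long-term, and send it to a scale whose own instruction excludes it. Sections 6.3 and 6.6 call the same event short-term, and section 8 grades it by CTCAE v3.

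Morbidity and treatment-related toxicity is the first secondary endpoint in 2.3, and avoiding the morbidity of extensive surgery is central to the rationale in 1.6. The study is multi-centre, and investigators enter the data on paper forms. If centres follow different sections, the short- and long-term rates will mix definitions, and the worst event per patient required by section 8 may have to be chosen from grades on two scales that do not mean the same thing. An analysis plan cannot fully repair this later, because a grade recorded on one scale does not convert to the other.

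**Working it through.** There is no sample size, power or alpha figure to reproduce. The check compares time windows and then applies each rule to the same events.

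**Step 1: visit days against the limit of the late scheme.** Visit weeks are from 6.3 and Table 6.6; the limit of more than 90 days is from Addendum 3.

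- 4 × 7 = 28 days, not above 90
- 8 × 7 = 56 days, not above 90
- 12 × 7 = 84 days, not above 90
- The limit itself is 90 / 7 = 12.9 weeks.

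So all three early visits lie after the point where 7.3 begins and before the point where its scale begins.

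**Step 2: three illustrative new-onset events under each rule.** Days count from the end of radiochemotherapy. Section 5.3.2 allows groin dissection 8-12 weeks after radiotherapy, that is days 56 to 84; the third event uses day 56.

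| Rule | Desquamation, day 28, never admitted | Leg edema, day 84, never admitted | Wound infection in hospital after groin dissection on day 56 |
|---|---|---|---|
| 2.2 (kind) | short | long | short |
| 6.3 / Table 6.6 | short | short | short |
| 6.4 / 6.5 (discharge) | no time origin | no time origin | not yet long |
| 7.2 | not short: after radiotherapy | not short: after radiotherapy | short: before discharge |
| 7.3 | long | long | long: after radiochemotherapy |
| Scale under 7.3 | late scheme, excluded by Addendum 3 | late scheme, excluded by Addendum 3 | late scheme, excluded if onset is by day 90 |
| Scale under 7.2 (any toxicity) and section 8 | CTCAE v3 | CTCAE v3 | CTCAE v3 |

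Each event receives conflicting classes and two competing scales. The third meets 7.2 and 7.3 at once, because both definitions join the end of treatment and discharge with an unexplained \"or\".

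**Step 3: which events are caught.** Section 7.3 covers morbidity that develops after treatment. A skin reaction that began during radiotherapy and is still present at week 4 is not new, so it stays short-term under 7.2. The conflict concerns new onset between the end of radiochemotherapy and day 90.

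**Step 4: size.** Three of three early visits lie in the disputed window. That counts visits. The Protocol gives no expected number of new events in the window, so no misclassification rate can be derived.

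**The case against.** The strongest counter-case is that the schedule in Table 6.6 already comes close to a 90-day split. Short-term morbidity is marked at weeks 4, 8 and 12, and long-term morbidity only at the three-monthly visits. If three months is counted from the end of treatment, the first of these falls at about 365.25 / 4 = 91 days. A centre working from the table would seldom use the late scheme too early. This is fair, and it shows which boundary the authors probably intended. But 7.2 and 7.3 are the sections that define the terms, and they say something else.

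Several stronger readings are tempting and are not supported:

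- **That events before day 90 cannot be graded.** Sections 7.2 and 8 give them CTCAE v3 without a time limit. The defect is two instructions for the same event, not the absence of one.
- **That acute reactions are uniformly put in the wrong endpoint.** Section 2.3 lists morbidity as a single item, and 2.2, 6.3 and 6.6 treat desquamation as short-term. Only the wording of 7.2 and 7.3 points the other way.
- **That every planned post-treatment short-term assessment becomes long-term.** Section 7.3 reclassifies new events, not visits, and Table 6.6 also marks short-term morbidity after secondary surgery, where the discharge limb of 7.2 still applies.
- **That long-term morbidity is inflated by transient reactions.** Section 2.2 places the long-term evaluation at 24 months, and 7.4 has morbidity described at the two-year visit. Reactions that have resolved by then would not count there.
- **That the late scheme cannot take lymphedema or infection.** They have no row of their own, but the Radiation-Other row can hold them. This is a weakness in precision, not a gap.

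**Conclusion.** The concern holds as an internal contradiction. For morbidity that first develops between the end of radiochemotherapy and day 90, the Protocol gives incompatible classes and two scales, one of which excludes these events by its own terms. Short- and long-term morbidity rates will depend on which section a centre follows. The direction of any bias is not determined, and its size cannot be calculated from the document.

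The effect is limited to a secondary endpoint. The primary endpoint, the sample size and the two-stage rule do not depend on it. It should be corrected because the conflict lies in written rules that investigators apply when they record grades. The conclusion assumes that the case report form, which is not shown, does not already impose a single boundary and scale. If it does, the sections still need to be brought into line with it.

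**What to change.** Use one boundary and one scale per window, in the same words, in 2.2, 6.3 to 6.6, 7.2, 7.3, section 8 and the CRF:

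- **Short-term:** from the start of radiochemotherapy to 90 days after the last radiotherapy fraction, plus the post-operative period after any surgery, graded by CTCAE v3. State how long the post-operative period lasts and that it takes precedence when surgery falls after day 90.
- **Long-term:** onset or persistence beyond 90 days, graded by the RTOG/EORTC late criteria. Including persistence is a change, since 7.3 now covers only morbidity that develops after treatment. State that a persisting event is graded again on the late scheme once it passes the boundary.
- **Items without their own row**, such as lymphedema and infection: name one scale in advance, either the Radiation-Other row or CTCAE v3, and use it at all centres.
- **Hospital discharge:** drop it as the time origin for patients who were not admitted.
- **Section 8:** say that worst grades are reported separately by window, so that grades from the two scales are not ranked together.

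The cost is Protocol and CRF wording. No visit or procedure is added.
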